Scientific Premise for AIM 2: AIM 2 is based on the scientific premise that anticipatory precontraction of the cervical muscles to brace for an impact influences head acceleration. Furthermore, cervical muscle attributes (i.e., neck strength and cervical muscle volume) influence head acceleration differently with vs. without cervical muscle pre-contraction. This premise is supported by our own work demonstrating that head acceleration, again reported as  $\Delta V$  and  $\Delta \omega$ , decreased by 12.3% and 9.7%. respectively, during anticipatory cervical muscle pre-contraction as compared to relaxed, upright sitting. Recent finite element modeling work, as well as numerous other studies in the concussion and whiplash literature, have also reported decreased head acceleration in response to various forms of loading during trials with vs. without anticipation and/or cervical muscle pre-contraction. However, the design of those studies limits the insight they can provide into which cervical muscle attribute is most responsible for controlling head acceleration with vs. without anticipatory pre-contraction. While not the primary objective, our previous work demonstrated greater neck strength and circumference were each significantly associated with lower  $\Delta V$  and  $\Delta \omega$  across all directions of head motion under both anticipation conditions (r= .42 to r= .60 for neck strength; r= .60 to r= .76 for neck circumference). In that study, more of the variability in head acceleration was explained by neck strength for 6 of the 7 models under the anticipated condition, but by neck circumference for 6 of the 7 models without anticipation. That finding suggests neck strength and cervical muscle volume may influence head acceleration differently depending on cervical muscle pre-contraction status. We are unaware of other reports to directly quantify the relationships between individual cervical muscle attributes and head acceleration with vs. without anticipatory cervical muscle pre-contraction.

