The premise that neck strength and cervical muscle volume may exert differential influences on head acceleration during anticipated vs. unanticipated impacts is further supported when considering each potential cervical contributor to head acceleration. Previous work concluded that since the mechanical properties of the neck's non-contractile tissues (e.g., bone, ligament) are not affected by muscle activation, and because peak head acceleration is reached before either a reflexive or voluntary muscular response has had time to occur, head acceleration is primarily influenced by the mechanical properties of the cervical muscles. Passive muscle stiffness is strongly influenced by the amount of muscle tissue being acted upon. In contrast, the stiffness of actively contracting muscle increases proportionally with muscle activation and torque. Therefore for any volume of cervical muscle, greater neck strength (i.e., torque generation) associated with improved neuromuscular recruitment is expected to confer greater muscle stiffness during maximal anticipatory cervical muscle pre-contraction to brace for the impact. While muscle strength and volume co-vary, these characteristics are known to change independently from one another with aging, disuse, and of greater direct applicability to this proposal, following resistance training. There remains a knowledge gap in how individual cervical muscle attributes affect head acceleration during sport-associated impacts with vs. without anticipatory cervical muscle pre-contraction to brace for the impact.

AIM 2 will directly address this knowledge gap by comparing the relative weights of neck strength and cervical muscle volume in predicting net head acceleration during anticipated and unanticipated impacts to the head and body.

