## 9.2 SAMPLE SIZE DETERMINATION

Our power calculation is based on AIM 1. Assuming net head acceleration (on the logarithmic scale) will follow linear trends over time, then our power calculation is based on comparison of the slope of this change, which has 9/14 of the variance, i.e., 36% less variance, than the underlying log(net head acceleration) measurements. As a result, the standardized effect size (Cohen's d value) of the slope is approximately 1.25 times greater than that of the underlying log(net head acceleration) measurements. Based on our own pilot data, we expect observed standardized effect sizes to be between .6 and 1.0 for log(net head acceleration), depending on the variability of the individual measurements across the 4 directions of motion. These values correspond with a 20% overall reduction in un-transformed net head acceleration. A total of 30 subjects in each exercise group (control and high intensity), will provide power of between .83 [for standardized effect size for log (net head acceleration) of .6 and 1.0 [for standardized effect size in the population. To account for the possibility of a drop-out rate of up to 20%, we will plan to enroll up to a total of 72 subjects.

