## 9.4.6 SUB-GROUP ANALYSES

We will include sex as a covariate in the statistical models, as well as explore possible interactions between sex and other independent variables, to identify any sex-based differences in the relationship between exercise volume load and the net head acceleration outcome.

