## 9.4.8 EXPLORATORY ANALYSES

We will construct linear models with net head acceleration as the outcome and combinations of neck strength and/or cervical muscle volume as the predictor(s) for direct and indirect force application under both the anticipated and unanticipated conditions. Rather than comparing the B coefficients of the neck strength and cervical muscle volume terms, which are scale-dependent, we will instead quantify the impact of each cervical covariate on net head acceleration by calculating the differences in  $R^2$  values of statistical models with vs. without each cervical variable. These differential  $R^2$  values indicate the importance of each cervical variable in the model, accounting for the other. There is no known analytic solution in the statistical literature to confirm statistically whether one differential R^2 value is higher than the other unless the null hypothesis is zero differential R^2, which is not the case here. Instead, we will use the bootstrap as a nonparametric tool to assess the variability in the differential R^2 values. By bootstrapping the subjects a sufficient number of times, we can obtain a set of differential R^2 values and use them to construct 95% confidence intervals around the differential R^2 values of both cervical variables during the anticipated and unanticipated conditions. If the confidence intervals are non-overlapping, we will conclude that the cervical variable associated with a greater decline in R^2 value upon its removal from the full model is significantly more impactful on the net head acceleration for the given anticipation condition.

We will compare the magnitudes of the B coefficients associated with each cervical independent variable at each time point in the linear mixed model analyses predicting log(net head acceleration). The effect of neck strengthening exercise on the exploratory net head acceleration during soccer heading outcomes will be analyzed using a similar statistical analysis plan as described above in Section 9.4.2.

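### AIM 2 should compare strength with volume through an interval for the difference in differential R², not by whether two separate 95% intervals overlap

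*Combined protocol and SAP*

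**What the plan says.** Section 9.4.8 fits linear models for net head acceleration on neck strength, cervical muscle volume or both, under direct and indirect loading, with and without anticipation. The importance of each variable is the fall in R² when it leaves the full model (its differential R²).

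On uncertainty the section says: "By bootstrapping the subjects a sufficient number of times, we can obtain a set of differential" R² values. These give one 95% interval per variable. Neither the number of resamples nor the type of bootstrap interval is stated.

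The decision rule follows: "If the confidence intervals are non-overlapping, we will conclude that the cervical variable associated with a greater decline in" R² has a significantly larger influence for that anticipation condition. No interval for the difference between the two values is planned.

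The section also says "We will compare the magnitudes of the B coefficients associated with each cervical independent variable at each time point" of the mixed models, but gives no criterion for that comparison. For the R² question it sets coefficients aside: "Rather than comparing the B coefficients of the neck strength and cervical muscle volume terms, which are scale-dependent". The overlap rule is therefore the only stated significance criterion.

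Section 9.4.1 sets alpha at .05. Section 9.4.6 adds: "We will include sex as a covariate in the statistical models". Section 9.2 bases the sample size on AIM 1 alone and says "we will plan to enroll up to a total of 72 subjects".

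**The concern.** The claim is about a difference between two quantities, but the rule never estimates that difference. Requiring two separate 95% intervals to be disjoint does not give a 5% test. It also discards the covariance between two values calculated on the same athletes, which most naturally means in the same resamples. The real error rate then depends on the strength-volume correlation, for which the documents give no figure; Section 2.2 says only "While muscle strength and volume co-vary, these characteristics are known to change independently from one another".

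What is at stake is the comparison that AIM 2 exists to make. An overlap result would be hard to interpret because nobody knows at what level the comparison was tested, and some real differences could be missed.

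**Working it through.** **1. The plan's own power figure.** Section 9.2 gives power of .83 for AIM 1 with 30 per group, d = .6 and a slope multiplier of 1.25. The slope effect is .6 × 1.25 = .75, and power = Φ(.75 × √(30/2) − 1.96) = Φ(.945) = .828. The figure reproduces. There is no matching figure for the AIM 2 rule.

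**2. What the difference is.** With S for strength and V for volume, differential R²(S) = R²(full) − R²(V only), and differential R²(V) = R²(full) − R²(S only). Subtracting the second from the first, the full-model terms cancel and leave R²(S only) − R²(V only). The same cancellation holds when sex is in every model. The difference is therefore available in every resample.

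**3. Size of the overlap rule, normal theory.** The intervals are disjoint when the estimates differ by more than 1.96 × (SE₁ + SE₂). Under equal true importance the size is 2 × [1 − Φ(1.96 × (SE₁ + SE₂) / SD(difference))]. With equal SEs and correlation ρ between the two estimates, the argument of Φ is 3.92 / √(2(1 − ρ)):

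| ρ | Size |
|---|---|
| +.5 | 0.01% |
| 0 | 0.6% |
| −.5 | 2.4% |
| −1 | 5% |

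The rule reaches 5% only at the limit ρ = −1.

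**4. Simulation inputs.** Data are trivariate normal, one record per athlete, with subjects resampled. At n=60 (the 30 per group of Section 9.2) there were 1,000 resamples and 1,500 trials. Correlations with the outcome lie within the ranges in Section 2.2: "r= .42 to r= .60 for neck strength; r= .60 to r= .76 for neck circumference". Circumference stands in for volume. The strength-volume correlation is assumed. Monte Carlo standard error is about 1 point for power and 0.5 to 0.6 for null rates.

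**5. Error rate under equal importance, n=60** (outcome correlations .5 and .6; strength-volume correlation .3, .6 and .8):

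| Rule | Error rate |
|---|---|
| Non-overlap | 1.2–4.3% |
| 95% percentile interval of the difference | 5.9–7.3% |
| 97% percentile interval of the difference | 3.8–5.0% |
| Simple bias-corrected 95% interval | 7.1–8.8% |

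A wider grid (outcome correlations .3 to .7, strength-volume correlation .3 to .85, n=60 and 72) gave 0.0–4.7% for non-overlap and 3.5–7.3% for the 95% interval. The within-resample correlation between the two values ran from −.66 to +.31.

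**6. Detection at n=60 (%).**

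| Outcome r: strength vs volume | Strength-volume r | Non-overlap | 95% interval | 97% interval |
|---|---|---|---|---|
| .42 vs .60 | .3 | 23 | 32 | 27 |
| .42 vs .60 | .5 | 31 | 40 | 33 |
| .42 vs .60 | .6 | 36 | 47 | 40 |
| .42 vs .60 | .7 | 35 | 60 | 52 |
| .50 vs .60 | .6 | 17 | 22 | 17 |
| .50 vs .60 | .7 | 15 | 24 | 18 |
| .50 vs .60 | .8 | 12 | 33 | 26 |
| .60 vs .76 | .3 | 31 | 43 | 36 |
| .60 vs .76 | .5 | 39 | 48 | 40 |
| .60 vs .76 | .7 | 63 | 67 | 61 |

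Against the 95% interval the loss is 5 (22 − 17) to 12 (43 − 31) points at .3 to .6, and 4 (67 − 63) to 25 (60 − 35) points at .7 to .8. Against the 97% interval it is 0 (17 − 17) to 5 (36 − 31) points at .3 to .6, and −2 (61 − 63) to +17 (52 − 35) points at .7 to .8. In the .50 vs .60, r .8 row the relative loss is (33 − 12)/33 = 64%.

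**7. Variants.** At n=72, non-overlap against the 95% interval gives 48 vs 67% (.42/.60, r .7), 20 vs 39% (.50/.60, r .8) and 70 vs 75% (.60/.76, r .7). With sex in all models at n=60, assuming a 1 SD sex shift in the outcome and both predictors, it gives 28 vs 41% (.42/.60, r .5), 32 vs 61% (.42/.60, r .7) and 10 vs 33% (.50/.60, r .8). The null rates there (.5/.5, r .6) are 2.0% vs 5.7%.

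**The case against.** The strongest reply is that the overlap rule is safe. SD(difference) cannot exceed SE₁ + SE₂, so under normal theory its size never passes 5%, and no simulated setting did. The 95% percentile interval, by contrast, runs above the plan's alpha. The fair comparator is then the 97% interval, where the gain is small at moderate correlation. All of this stands.

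It can also be said that the large losses need inputs that sit badly with the protocol's premise that strength matters at a given volume. At .42/.60, r .7, strength's standardised coefficient is zero (.42 − .7 × .60 = 0). At .50/.60, r .8, it is (.50 − .48)/.36 = .056. At n=72, non-overlap against the 97% interval differs materially only in those two settings (48 vs 60% and 20 vs 34%); elsewhere it is 38 vs 39%, 47 vs 49%, 20 vs 22% and 72 vs 70%. This also stands. The relative loss of more than half is an n=60 result at a strength-volume correlation of .8; at n=72 it is (39 − 20)/39 = 49% against the 95% interval and (34 − 20)/34 = 41% against the 97% interval.

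The Section 2.2 ranges are an imperfect anchor. Strength at .60 or less and circumference at .60 or more would never let strength explain more, yet Section 2.2 reports that it did in 6 of 7 anticipated models. The magnitudes are therefore indicative.

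Finally, the plan draws no conclusion from overlap. That is true, but a non-significant result will still be reported, and its test level would be unknown. None of these points gives a reason to prefer an indirect rule when the direct quantity is already in the resamples.

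**Conclusion.** The concern holds, as a cheap improvement to an exploratory analysis. The rule does not test the difference it makes a claim about, and its error rate floats between about 0% and 5% with quantities the documents do not give. It errs on the conservative side, so any significant claim it yields is not inflated. The primary and secondary endpoints are untouched.

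The power cost is modest at low or moderate strength-volume correlation and mostly disappears once the error rates are matched. It becomes substantial only at about .7 to .8, and not in every setting there. These sizes assume normal data, one record per athlete, circumference as a proxy for volume, and an assumed strength-volume correlation. The flaw in the rule itself does not depend on those assumptions.

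**What to change.** Replace the overlap sentence in Section 9.4.8. In each bootstrap resample, compute differential R² for strength minus differential R² for volume, with the same other covariates (such as sex) in every model. Report the 95% percentile interval of that difference for each loading and anticipation condition. Conclude that one variable is more influential only if the interval excludes zero. State the number of resamples, and state that the interval is mildly liberal at this sample size. If an error rate of 5% or less is wanted, pre-specify a 97% interval instead. The simple bias-corrected interval did not help.

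The cost is one sentence and one line of code on resamples already planned. The trade-off is that the 95% version runs at about 6 to 7% at n=60, while the 97% version corrects this but gives up most of the power gain when the strength-volume correlation is .6 or lower.

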## **10 SUPPORTING DOCUMENTATION AND OPERATIONAL CONSIDERATIONS**

## 10.1 REGULATORY, ETHICAL, AND STUDY OVERSIGHT CONSIDERATIONS

## **10.1.1 INFORMED CONSENT PROCESS**

## 10.1.1.1 CONSENT/ASSENT AND OTHER INFORMATIONAL DOCUMENTS PROVIDED TO PARTICIPANTS

IRB-MED-approved informed consent forms describing in detail the study intervention, study procedures, and risks will be given to each participant and written documentation of informed consent (or assent with parent/guardian consent) will be obtained prior to starting intervention/administering study intervention.

#### **10.1.1.2 CONSENT PROCEDURES AND DOCUMENTATION**

A waiver of informed consent for screening purposes will be obtained from IRB-MED to allow potential participants to be screened for study eligibility prior to undergoing the informed consent process in an effort to save ineligible individuals from the inconvenience of unnecessary study-related procedures if they are not eligible to participate in the study. Those individuals who are eligible and interested in participating in the study will complete the informed consent (or assent with parent/guardian consent for minors) process in person with the PI, or a designated member of the study team.

Informed consent (or assent with parent/guardian consent for minors) is a process that is initiated prior to the individual's agreeing to participate in the study and continues throughout the individual's study participation. Consent/Assent forms will be UM Institutional Review Board (IRBMED)-approved and the participant (and parent/guardian for minors) will be asked to read and review the document. A member of the study team will explain the research study to the participant (and parent/guardian for minors) and answer any questions that may arise. A verbal explanation will be provided in terms suited to the participant's (and parent's/guardian's for minors) comprehension of the purposes, procedures, and potential risks of the study and of their rights as research participants. Participants (and parent/guardian for minors) will have the opportunity to carefully review the written consent form and discuss/ask questions prior to signing. All participants, regardless of age, will have the opportunity to discuss the study with their family or surrogates or think about it prior to agreeing to participate. The participant will sign the informed consent document (or assent document with the parent/guardian signing the consent document) prior to any procedures being done specifically for the study. Participants (and their parent/guardian for minors) will be informed that participation is voluntary and that they may withdraw from the study at any time, without prejudice. A copy of the informed consent/assent document will be given to the participants for their records. The informed consent/assent process will be conducted and documented in the source document (including the date), and the form signed, before the participant undergoes any study-specific procedures. The rights and welfare of the participants (and their parent/guardian for minors) will be protected by emphasizing to them that the quality of their medical care will not be adversely affected if they decline to participate in this study. Any children who become adults during the course of the study will not be re-consented after their 18th birthday.

#### **10.1.2 STUDY DISCONTINUATION AND CLOSURE**

Participant confidentiality and privacy are strictly held in trust by the study team. This confidentiality is extended to cover biological imaging results in addition to the clinical information relating to participants. Therefore, the study protocol, documentation, data, and all other information generated will be held in strict confidence. No information concerning the study or the data will be released to any unauthorized third party without prior written approval of IRB-MED.

All research activities will be conducted in as private a setting as possible.

The study monitor, other authorized representatives of the UM Institutional Review Board (IRB-MED), members of the DSMB, or other regulatory agencies may inspect all documents and records required to be maintained by the investigator for the participants in this study. The study site will permit access to such records.

The study participant's contact information and research data, which is for purposes of statistical analysis and scientific reporting, will be securely stored at the University of Michigan for internal use during the study. At the end of the study, all records will continue to be kept in a secure location for as long a period as dictated by IRB-MED and Institutional policies. At the end of the study, the study database will be de-identified and stored at the University of Michigan.

The study team will not apply for a Certificate of Confidentiality for this study.

# 10.1.3 FUTURE USE OF STORED SPECIMENS AND DATA

Data collected for this study will be analyzed and stored at the University of Michigan. After the study is completed, the data will be de-identified and archived for potential use in the future by the study team. Permission to store de-identified data will be included in the informed consent. A copy of MRI data will also be maintained in the research section of participants' electronic medical records at the University of Michigan/Michigan Medicine.

When the study is completed, the study team will maintain access to de-identified study data.

## 10.1.5 SAFETY OVERSIGHT

Safety oversight will be under the direction of a Data and Safety Monitoring Board (DSMB) composed of 3 individuals with the appropriate expertise, including biostatistics, pediatric neurosurgery, and pediatric sports medicine. Members of the DSMB will be independent from the study conduct and free of conflict of interest. The DSMB will meet annually to assess safety and efficacy data on each arm of the study. The DMSB will operate under the rules of an approved charter that will be written and reviewed at the organizational meeting of the DSMB. At this time, each data element that the DSMB needs to assess will be clearly defined. The DSMB will provide its input to the PI and the National Institutes of Health Program Officer assigned to this project.

# 10.1.6 CLINICAL MONITORING

Clinical study monitoring will be conducted to ensure that the rights and well-being of trial participants are protected, that the reported trial data are accurate, complete, and verifiable, and that the conduct of the trial is in compliance with the currently approved protocol/amendment(s), with good clinical practice, and with applicable regulatory requirement(s).

Monitoring for this study will be performed by the Michigan Institute of Clinical and Health Research. Clinical monitor responsibilities will include:

- Review of study documents, creation of the Clinical Monitoring Plan (CMP), and on-site study initiation visit prior to the start of enrollment
  - The CMP will describe in detail who will conduct the monitoring, at what frequency monitoring will be done, at what level of detail monitoring will be performed, and the distribution of monitoring reports.
- On-site and/or virtual interim data and regulatory monitoring visits approximately every 6 months throughout the trial with review of approximately 50% of enrolled participants' charts.
- On-site study close-out visit upon completion of the trial.
- Provision of copies of monitoring reports to the PI and study coordinator/program manager within 14 days of visit.
- Planned independent audits will not be conducted outside of the CMP, although it is possible that a random audit could be scheduled by the University of Michigan Office of Research Compliance Review (OCRC).

